2 GLOSSARY OF ABBREVIATIONS

AE	Adverse Event
AR	Adverse Reaction
BTC	Bristol Trials Centre
CI	Chief Investigator
CRF	Case Report Form
CTU	Clinical Trials Unit
DMC	Data Monitoring Committee
DSA	Data Sharing Agreement
DSUR	Development Safety Update Report
EC	European Commission
EPR	Electronic Patient Record
EU	European Union
GCP	Good Clinical Practice
GDPR	General Data Protection Regulation
HRA	Health Research Authority
HRQoL	Health Related Quality of Life
ISRCTN	International Standard Randomised Controlled Trials Number
ITT	Intention to Treat
MLTC	Multiple Long-term Conditions
NIHR CRN	National Institute of Health Research Clinical Research Networks
NICE	National Institute for Health and Care Excellence
PI	Principal Investigator
PIL	Participant Information Leaflet
PLR	Personal Legal Representative
PPI	Patient and Public Involvement
PPIE	Patient and Public Involvement and Engagement
QALY	Quality Adjusted Life Years
RCT	Randomised Control Trial
RDSF	Research Data Facility Storage
REC	Research Ethics Committee
RSI	Reference Safety Information
SAE	Serious Adverse Event
SAR	Serious Adverse Reaction
SOP	Standard Operating Procedure
SUSAR	Suspected Unexpected Serious Adverse Reaction
TMF	Trial Master File
TMG	Trial Management Group
TSC	Trial Steering Committee

3 TRIAL SUMMARY

Trial Title	Randomised Evaluation of incentive Spirometry in OLder adults with rib fractures to preVEnt pulmonary complications	
Short title	RESOLVE	
Chief Investigator	[name]	
Joint Lead	[name]	
Sponsor	North Bristol NHS Trust (R&D)	
Funder	National Institute for Health and Care Research (NIHR) Research for Patient Benefit (RfPB) Programme	
Trial Design	Prospective multicentre parallel group randomised controlled superiority trial	
Trial Participants	Adults aged ≥ 65 years presenting to UK Emergency Departments with traumatic rib fracture(s)	
Target sample size	276	
Target number of study sites	12	
Intervention	Incentive spirometry (and usual care)	
Treatment duration	Minimum 72 hours	
Inclusion criteria	
 • Aged ≥ 65 years • Radiological evidence of acute rib fracture(s) • Planned for admission • Has capacity to provide informed consent or personal consultee/legal representative available and able to support use of incentive spirometer 	
Exclusion criteria	
 • Co-existing injury or condition for which treating clinician deems patient unable to use incentive spirometer (e.g. facial injuries; burns to both hands; advanced dementia) • Patients who have SpO₂ <92% on air at time of screening (<88% for known chronic lung disease) • Intubated • Haemodynamic instability (e.g severe hypo- or hypertension, significant atrial/ventricular arrhythmia) • History of eye, inner ear or brain surgery within previous four weeks (Contraindication to using incentive spirometry) • 	
	Objectives	Outcome measures
Primary outcome	Onset of new pulmonary complications within 5 days of randomisation	Patient medical notes/EPR (see 6.6.1 for further detail) GP records*

Secondary outcomes	Patient reported breathlessness at 5 days (+2)	The Dyspnea-12 Questionnaire
	Patient reported pain at 5 days (+2)	Numeric Pain Rating Scale
	Length of stay up to 30 days post randomisation	Patient medical notes/EPR
	Admission to Critical Care/ICU up to 30 days post randomisation	Patient medical notes/EPR
	Mortality up to 30 days post randomisation	Patient medical notes/EPR
	Hospital readmission rates up to 30 days post randomisation	Patient medical notes/EPR
Internal pilot	Internal pilot progression criteria will be reviewed after 4 months of active recruitment. See section 6.3 for further detail.	
Study duration	Grant contract start date: 01 August 2025 Anticipated duration: 26 months Anticipated end date: 30 th September 2027	

*For the small number of patients discharged within 5 days of randomisation, GP records will be checked for antibiotic prescription for pulmonary related events

3.1 Plain English Trial summary

Aim: To see whether a device that helps with breathing exercises can improve recovery for older people when they are taken to hospital with broken ribs.

Background: Thousands of older people are taken to hospital each year with broken ribs. They are painful and can make it harder to take a deep breath or cough. Over half of older people with broken ribs develop problems, like chest infections, because they can't take deep breaths. We think that a breathing exercise device called an 'incentive spirometer' may help to prevent these problems. The incentive spirometer helps people take a deeper breath. Incentive spirometers are already given to some patients who have had an operation. They aren't used everywhere for patients with broken ribs because we don't know yet whether they help with recovery.

Design: We will ask 276 older patients in hospital with broken ribs to take part in this project. We will split them into two groups by chance. Both groups will be treated in the normal way whilst in hospital, including being taught breathing exercises, but one group will also be given an incentive spirometer to use. We will ask this group to try and use the incentive spirometer regularly through the day for at least the first 3 days after they come into hospital. We will ask permission from patients (or their carers) to collect information from their hospital notes about their recovery. We will look to see whether people who use the device get fewer problems, like chest infections, in the first 5 days after they came into hospital. We will also ask everyone to complete questionnaires to see how well they are recovering.

Patient and public involvement: We have listened to the views of older patients who have had broken ribs and taken part in research. This has helped make sure our work is useful and easy for older people to take part in. We have tried the incentive spirometer with some older patients who enjoyed using it and tell us it doesn't make the pain from their broken ribs worse. We also have an active patient group who have agreed to continue helping with this project. They will work with us to make sure our research will benefit patients.

Dissemination: We will write up the results and publish them in journals that are read by hospital staff so that they can learn about our work. We will also share the results at healthcare conferences to help make more hospital staff aware of the results. We will also let patients know about the results and our patient group will help us to understand the best ways to do this.

4 BACKGROUND AND RATIONALE

Trauma in older patients presents a significant challenge to healthcare systems ⁽¹⁾. Over 60,000 patients aged ≥ 65 years are admitted to UK hospitals each year having sustained injury after a fall ⁽²⁾. In those admitted to Major Trauma Centres over 20% have sustained a chest injury ⁽³⁾. Pain from rib fractures, and underlying lung injuries, impacts the mechanics of breathing. This results in ineffective ventilation, lung collapse, and impaired cough/secretion clearance all of which increase the risk of pulmonary complications ⁽⁴⁾. Coexisting injuries, common after falls, can also restrict mobility, potentially predisposing trauma patients to greater risk of pulmonary complications. In our recent feasibility trial in older people admitted to hospital with rib fractures (median age 83 years), we found that $>50\%$ of patients went on to develop pulmonary complications, such as pneumonia ⁽⁵⁾. Our systematic review of 73 observational studies demonstrated that the odds of mortality after rib fractures were significantly greater in adults aged ≥ 65 years ⁽⁶⁾.

Incentive spirometers are simple handheld devices that encourage patients to take sustained deep breaths to increase lung volume, optimise collateral ventilation and mobilise secretions. These are well recognised strategies aimed at reducing pulmonary complications. Whilst similar physiological effects can be achieved through breathing exercises alone, incentive spirometers incorporate visual volume and feedback markers (smiley face) and have been found to improve inhalation volumes, flow control and enthusiasm to undertake regular breathing exercises ⁽⁷⁾. Theoretically, this could lead to a greater reduction in pulmonary complications. Incentive spirometers are simple to use and have been well tolerated in the target population as part of our patient and public involvement (PPI) work.

We searched Medline, Embase and Emcare (all Ovid); CINAHL (EbscoHost) and Google for trials published from any time until 18th December 2023. We found one randomised controlled trial (RCT) comparing incentive spirometry and usual care in patients with rib fractures ⁽⁸⁾. They observed that incentive spirometry reduced pulmonary complication rates from 80% to 29% and led to a significant improvement in pre- and post-treatment lung function ($p<0.001$). However, generalisability is limited by a small sample ($n=50$) recruited at a single site in Taiwan and the mean age of participants was 55 years. A focus on older adults, who are more susceptible to pulmonary complications, is, therefore, lacking.

In a non-randomised interventional study ⁽⁹⁾ improved lung function and oxygen saturation levels were observed in patients with rib fractures treated with incentive spirometry. A small sample ($n=25$) and lack of randomisation increases susceptibility to selection bias and confounding. Dote et. al ⁽¹⁰⁾, investigating the effectiveness of incentive spirometry following trauma, found no significant difference in pulmonary complication rates between groups ($n=299$). As a retrospective observational study, findings are limited by an inherent risk of bias, with heterogeneity noted in the onset and frequency of intervention, and baseline characteristics of each group.

The use of incentive spirometers to prevent pulmonary complications has been evaluated extensively in the surgical population post-operatively ⁽¹¹⁻¹⁶⁾. This literature has shown little to no benefit but is of poor methodological quality. It also lacks a focus on older adults who we believe could see greater benefit due to their higher risk of pulmonary complications.

We surveyed Major Trauma Physiotherapists across 22 UK sites (March 2024) on therapeutic incentive spirometry use with older adults and found variation in practice. 10 sites stated that incentive spirometry was listed in their chest trauma care guideline and routinely used. Five sites reported that incentive spirometry was not listed in their guidelines. Seven sites did not have a guideline but five of these stated that incentive spirometry is used sporadically in this population. Some advocated benefits ("very helpful for creating independence with chest care") whilst others cited a lack of evidence to support effectiveness for not using.

4.1 Evidence explaining why this research is needed now

In 2022, the National Institute for Health and Care Excellence (NICE) produced guidelines for rehabilitation after injury (17). They suggest consideration of incentive spirometry to aid rehabilitation following chest trauma. However, that recommendation was based on NICE committee member's experience rather than high quality evidence. A global expert consensus panel also recommends use of incentive spirometry for early intervention (within 24 hours of presentation to an Emergency Department (ED)) for patients with rib fractures (18). There is currently a paucity of robust evidence evaluating the effectiveness of incentive spirometry in the older trauma population but there is signal of efficacy that a reduction in pulmonary complications will be seen.

Prevention of complications in patients with broken ribs, early involvement of physiotherapy to improve patient outcomes following major trauma and improving the care of older major trauma patients were all 2023 Major Trauma James Lind Association (JLA) research priorities (19). Optimising the management, clinical outcomes, and patient experiences of older, frail patients with injury was a 2022 JLA priority for Emergency Medicine (20). In addition, our PPI group tell us that more work is needed to improve outcomes after chest injury and recognise the need to test interventions that move beyond pain control. They recognise the potential for incentive spirometers to improve outcomes, following rib fractures, in a way that is simple and acceptable to patients.

Therapeutic use of incentive spirometers continues to be taught to undergraduate physiotherapists. Despite a lack of evidence to support use in the surgical population, continuing extensive use and a reluctance to change practice has been observed amongst clinicians (21). A high-quality trial is needed to either demonstrate a positive effect in the older adult trauma population or provide strong evidence to stop NHS investment in training, equipment and patient treatment time for an ineffective therapy.

5 RESEARCH QUESTIONS, OBJECTIVES AND OUTCOMES

5.1 Research questions

For patients aged ≥ 65 years, does incentive spirometry used as an adjunct to usual care after rib fracture reduce the incidence of pulmonary complications compared to usual care (without incentive spirometry)?

5.2 Primary objective

[figure not shown]
To compare the effect on pulmonary complications of usual care plus incentive spirometry compared with usual care without incentive spirometry, at 5 days post randomisation.

5.3 Secondary objectives

To compare the effect on patient reported outcome measures of breathlessness and pain 5 days post randomisation, and the length of initial hospital stay, the rate of admission to critical care, mortality and hospital readmission rates within 30 days of randomisation.

6 TRIAL DESIGN AND SETTING

6.1 Trial schema

6.2 Trial design

Pragmatic, multicentre, open-label, parallel two-group randomised controlled superiority trial. Older adults being admitted with traumatic rib fractures will be randomly assigned in a 1:1 ratio.

6.3 Internal pilot

The internal pilot progression criterion will be reviewed after the first four full months of active recruitment, with the criteria and thresholds for progression shown in Table 1.

Table 1: Internal pilot assessment criteria

Progression Criteria	Target	Green	Amber	Red
Site opening	100%	100% (n=4)	50-99% (n=2-3)	<50% (n=<2)
Total number of participants recruited	100%	100% (n=70)	50-99% (n=35-69)	<50% (n=<35)

If all criteria are Green, the trial will continue to the main recruitment phase as planned. If any of the criteria are in the Amber or Red zones, the Trial Management Group (TMG) will consider actions that could be taken to improve performance. If these steps are supported by the Data Monitoring and Trial Steering Committee (DMSC/TSC) and funder, the trial will proceed with regular monitoring. In the event of an issue arising that cannot be remedied, the funder may decide to terminate the trial.

6.4 Setting

The trial will recruit patients from 12 NHS hospitals across the UK (mix of Major Trauma Centres and Trauma Units).

6.5 Trial population

Adults ≥ 65 years being admitted to hospital with acute traumatic rib fracture(s).

6.5.1 Eligibility criteria

6.5.1.1 Inclusion criteria

Participants may enter the study if ALL of the following apply:

- Aged ≥ 65 years
- Radiological evidence of acute rib fracture(s)
- Planned for admission
- Has capacity to provide informed consent or personal consultee/legal representative available and able to support use of incentive spirometer

Exclusion criteria

Participants may not enter the study (i.e. may not be randomised) if ANY of the following apply:

- Co-existing injury or condition for which treating clinician deems patient unable to use incentive spirometer (e.g. facial injuries; burns to both hands; advanced dementia)
- Patients who have SpO₂ $<92\%$ on air at time of screening (<88% for known chronic lung disease)
- Intubated

- Haemodynamic instability (e.g severe hypo- or hypertension, significant atrial/ventricular arrhythmia)
- History of eye, inner ear or brain surgery within previous four weeks (Contraindication to using incentive spirometry)

6.5.2 Co-enrolment in other research studies

Co-enrolment will be considered on a study-by-study basis; decisions around co-enrolment will consider participant burden and whether the randomised interventions are distinct from those in this trial. Where trials with overlapping inclusion criteria are identified, we will work with the Research Delivery Networks (RDNs) and CIs and/or Principal Investigators (PIs) to ensure co-enrolment is in the best interest of patients.

6.6 6.6 Intervention

6.6.1 General information

Patients randomised to the intervention arm will be issued with an incentive spirometer as soon as is practical and immediate care needs have been addressed. Each participating hospital will procure its own devices to ensure the generalisability of results across diverse clinical settings and to streamline logistical coordination. Restrictions will not be placed on brand or manufacturer but data on the type of incentive spirometer (volume or flow) will be collected.

6.6.2 Staff teaching

A site initiation visit (likely remote but in person where feasible if preferred) will be held with each site prior to opening to recruitment. At least one member of local site staff delegated for intervention teaching responsibilities will also receive an additional training session in use of incentive spirometry by the central study team. Training will be offered in person or remotely depending on local site preference and previous experience using incentive spirometry. Training will include a standardised Powerpoint presentation (which can be retained by sites) and physical demonstration of the incentive spirometer. Whilst central teaching for additional site staff will be offered, a train-the-trainer model will be adopted enabling site staff to cascade the training to relevant local personnel if preferred. This local site lead 'trainer' should be a registered health care professional. Due to the simplicity of the intervention, a formal trainer manual is not required; but providers can request refresher training or rely on the patient education materials to guide implementation. Central study staff will also provide guidance to site personnel regarding management of devices once primary outcome data have been collected.

6.6.3 Participant teaching

At the time of issue, a trained and delegated member of local site staff will instruct the participant in use of the incentive spirometer, in accordance with the manufacturer's instructions. Participants will be advised to use the incentive spirometer at least three times during the day and will be encouraged not to interrupt sleep for use. Participants will be advised to use the device for the first 5 days following injury.

The initial training session will be supplemented with an optional training video that participants will be able to access via their own personal devices, if they wish, and a paper education leaflet. The leaflet will be available in larger font if required. For patients who cannot speak English research teams will be encouraged to use local translation services to support training and device use where feasible. Competence in use of the incentive spirometer, judged as ability to use the device correctly without prompts (or with prompts for those supervised by a carer/staff member), will be assessed at the time

by the trainer. Up to two additional teaching sessions are permitted to promote independent use. Timescales for delivery of the initial and subsequent participant teaching sessions are shown in the schedule of assessments (section 7.8). Participants who do not achieve independent use (or supported use from carers/site staff where resources allow) after two teaching sessions will not receive any more teaching sessions but will remain in the trial.

The intervention is additive to standard clinical management which may include analgesic intervention, breathing exercises and mobilisation.

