6.6.5 Adherence

A paper diary will be provided to participants in the intervention arm to record adherence to intervention use during their inpatient admission. These will be collected by local site staff on or after day 5 post randomisation, or on discharge, whichever is sooner, and data entered to the study database.

A CRF will also be provided to record any observed adherence, where feasible, in recognition of variable participant adherence to diaries in previous clinical trials (22). This includes any use of a spirometer in the participants randomised to the control arm (usual care). In cases where both participant diaries and staff-collected adherence data are available, participant entries will take precedence in the event of discrepancies; however, if only staff-collected data are complete, those will be used.

Participants in the intervention arm will be classed as adherent if they undertake a minimum of two incentive spirometer sessions a day, for a minimum of three days, in the five days post randomisation.

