6.7 Outcomes

6.7.1 Primary outcome

The primary outcome is a binary measure of the onset of one or more new pulmonary complications within five days of randomisation. This will be adapted from the outcome proposed by the European Society of Anaesthesiology and Intensive Care Medicine as a consensus definition (Table 2) (23). Patients with evidence of pulmonary complications prior to randomisation will not meet the primary outcome. Any deaths occurring within the first 5 days following randomisation will meet the criteria for the primary outcome.

Table 2: Pulmonary Complications

Complication	Definition
Respiratory Infection	Patient has received antibiotics for a suspected respiratory infection and met one or more of the following criteria: new or changed sputum, new or changed lung opacities, fever, white blood cell count $>12 \times 10^9 \text{ l}^{-1}$

Respiratory failure	PaO ₂ <8kPa (60mmHg) on room air, a PaO ₂ :FiO ₂ ratio <40kPa (300mmHg) or arterial oxyhaemoglobin saturation measured with pulse oximetry <90% (or <88% for patients with known chronic respiratory disease) and requiring oxygen therapy
Pleural effusion	Chest radiograph demonstrating blunting of the costophrenic angle, loss of sharp silhouette of the ipsilateral hemidiaphragm in upright position, evidence of displacement of adjacent anatomical structures or (in supine position) a hazy opacity in one hemithorax with preserved vascular shadows
Atelectasis	Lung opacification with a shift of the mediastinum, hilum or hemidiaphragm toward the affected area, and compensatory over-inflation in the adjacent non-atelectatic lung
Pneumothorax	Air in the pleural space with no vascular bed surrounding the visceral pleura
Bronchospasm	Newly detected expiratory wheezing treated with bronchodilators
Aspiration pneumonitis	Acute lung injury after the inhalation of regurgitated gastric contents

Primary outcome data will be collected by research practitioners from inpatient hospital records at five days and reviewed/confirmed by the local Principal Investigator. For the small number of patients discharged in the interim, online GP records (routinely available at recruiting sites) will be checked for evidence of pulmonary related events (e.g., pneumonia).

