7.3 Screening and identification of participants

Hospital staff will be asked to complete a trial-specific screening Case Report Form (CRF) for each patient aged ≥ 65 years admitted to that hospital with acute rib fracture(s) following blunt chest wall trauma.

Recruitment will be undertaken 24 hours a day, 7 days a week. Potentially eligible participants will be identified by clinical staff or research delivery staff (e.g. Research Nurses/Physiotherapists) at the time of arrival in ED or on/after transfer to inpatient settings (e.g. ward, acute medical/surgical assessment unit). Upon identifying a (potentially) eligible patient, a member of the clinical team or research practitioner will give the patient the written study Summary Participant Information Sheet (Summary PIS) and, where appropriate, the full Participant Information Sheet (Detailed PIS) (e.g. the patient has read the Summary PIS and requested further information and/or is suitably comfortable and able to read both documents at that time). We recognise that our target population is older adults. Patient information materials will therefore be available in a variety of formats, including paper (normal and large print) and video, as advised by our patient groups to maximise participation across all potentially eligible patients.

Patients will be given sufficient time to read/view the information material and ask any questions they may have about the trial. The length of time patients will have to consider participation will vary due to the nature of EDs and assessment pathways. If appropriate, consent can be received whilst the patient is still within the ED, however consent will not be taken until immediate care needs have been addressed. When considering participation in the emergency setting, patient consideration-time is estimated to be from one to four hours; this approach is considered acceptable by patients, as demonstrated by other ED-based research undertaken by our group (^{5,26}). If required, the participant can be given longer to consider involvement even if transferred to a ward. However, due to the need for early intervention, a maximum of 24 hours from admission to randomisation will be set (and written consent must be received prior to randomisation).

In patients without capacity, we will seek approval from a patient's personal consultee/legal representative (see section 7.6)

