11 ANALYSES

11.1 Statistical analysis

Analyses will be directed by a pre-specified Statistical Analysis Plan (SAP) and will be in line with CONSORT reporting guidelines for clinical trials. Participant flow will be reported in a CONSORT flow chart (²⁹). Participant baseline characteristics will be reported, overall and by randomised allocation, using descriptive statistics.

Continuous data will be summarised as mean and SD or median and inter-quartile range (IQR) if distributions are skewed. Categorical data will be summarised as number and percentages. The primary analysis will be conducted under the intention-to-treat approach, consisting of logistic regression of presence vs absence of pulmonary complications on allocation, adjusted for site, capacity status, and co-existing injury status (design variables). Results will be reported as an odds ratio with associated 95% confidence interval and p-value. Result will also be presented as an absolute difference and Number Needed to Treat for completeness. Secondary outcome analysis will be consistent with that described for the primary outcome, using a form of regression appropriate to the nature of the outcome being analysed (linear regression for continuous outcome, logistic regression for binary outcome etc), plus additional adjustment for baseline value of outcome where relevant. A repeat analysis of the primary outcome using a Complier Average Causal Effect analysis, with reporting of treatment effect based on adherence, will be considered. Sensitivity of the primary analysis to the impact of missing data will be explored.

Model validity will be checked using standard methods; if a model is a poor fit, alternative models or transformations will be explored.

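### Device use is advised for five days from injury, but the primary outcome and adherence windows run five days from randomisation, so advised use ends before the outcome window closes

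*Protocol*

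**What the plan says.** The protocol counts time from three different starting points.

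- **Injury.** Section 6.6.3: "Participants will be advised to use the device for the first 5 days following injury".
- **Randomisation.** The primary outcome in 6.7.1 is the "onset of one or more new pulmonary complications within five days of randomisation". Section 6.6.5 classes intervention participants as adherent if they complete "a minimum of two incentive spirometer sessions a day, for a minimum of three days, in the five days post randomisation".
- **Arrival in hospital.** The plain-English summary (3.1) speaks of regular use for at least three days, counted from when the patient comes into hospital.

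Four other provisions bear on how much advised use is left once a participant has the device:

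- The trial summary (section 3) gives the treatment duration as "Minimum 72 hours".
- Section 7.3: "due to the need for early intervention, a maximum of 24 hours from admission to randomisation will be set".
- The schedule in 7.8 places the initial teaching session at Day 0 with a tolerance of +2 days. Under 6.6.3, instruction is given when the device is issued, so taught use starts then.
- Section 6.6.1 wants participants "issued with an incentive spirometer as soon as is practical and immediate care needs have been addressed".

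The eligibility criteria (6.5.1) require the fracture to be acute but set no limit on the time from injury to admission. No section reconciles the three clocks.

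**The concern.** The instruction given to participants sets the intended dose, and it runs on a different clock from the outcome it is meant to influence. A participant who takes the advice literally may have stopped using the device while the outcome window is still open. If so, the contrast between arms late in the window is weaker than intended.

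Two further things are affected. The advice can leave less than the stated minimum treatment duration. It also reduces the slack against the three-day adherence rule, which matters because a repeat of the primary analysis "using a Complier Average Causal Effect analysis, with reporting of treatment effect based on adherence, will be considered" (11.1). If people who did what they were told were classed as non-adherent, that estimate would be inflated.

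**Working it through.** **Inputs.** Advised period: 120 hours from injury (6.6.3). Outcome window: 120 hours from randomisation (6.7.1). Stated minimum: 72 hours (section 3). Let *a* be hours from injury to admission (no limit stated, so values are assumed), *r* hours from admission to randomisation (at most 24; 7.3), and *t* hours from randomisation to first teaching (at most 48, reading the day-level +2 tolerance in 7.8 as 48 hours).

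**Formulas.**
- Advised hours left after teaching, injury clock: 120 − *a* − *r* − *t*
- Advised hours left after teaching, randomisation clock: 120 − *t*
- Gap between the end of advice and the end of the outcome window: *a* + *r*

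| *a* | *r* | *t* | Injury clock (h) | Randomisation clock (h) | Gap (h) |
|---|---|---|---|---|---|
| 0 | 24 | 0 | 96 | 120 | 24 |
| 0 | 24 | 24 | 72 | 96 | 24 |
| 0 | 24 | 48 | 48 | 72 | 24 |
| 0 | 0 | 48 | 72 | 72 | 0 |
| 12 | 24 | 48 | 36 | 72 | 36 |
| 24 | 24 | 0 | 72 | 120 | 48 |
| 24 | 24 | 48 | 24 | 72 | 48 |
| 48 | 24 | 48 | 0 | 72 | 72 |

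**Reading the table.** The teaching tolerance alone does not breach the minimum: 120 − 48 = 72. Reaching 48 hours needs the full 24-hour randomisation allowance as well: 120 − 24 − 48 = 48, which is 48/120 = 40% of the length of the outcome window. On the injury clock, 72 hours requires *a* + *r* + *t* ≤ 48. On the randomisation clock the latest teaching leaves 72 hours, equal to the stated minimum. The teaching tolerance and the minimum therefore agree on the randomisation clock and conflict on the injury clock.

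**Adherence in calendar days.** Take the case *a* = 0, *r* = 24, *t* = 48: injury on Day −1, randomisation on Day 0, teaching on Day 2. If the injury day is not counted, the five advised days are Days 0 to 4; Days 2, 3 and 4 remain, and the three-day rule can just be met. If the injury day is counted, they are Days −1 to 3; Days 2 and 3 remain, and the rule is missed by someone who follows the advice exactly.

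**Illustrations only.** The sample size reproduces: 50% versus 30%, two-sided 5%, 90% power gives 124 per arm, 248 in total; 248/0.9 = 275.6, so 276. Suppose a fraction *f* of the 20-point reduction were lost, so that intervention risk is 0.30 + 0.20*f*. With 124 per arm, power is 90.0% at *f* = 0, 88.7% at *f* = 0.02 (risk 0.304) and 86.6% at *f* = 0.05 (risk 0.310). For the complier analysis, assume true adherence of 80% and an intention-to-treat difference of 16 points, with a proportion *m* wrongly classed as non-adherent: 16/(0.80 − *m*) gives 20.0, 21.3 and 22.9 points at *m* = 0, 0.05 and 0.10. The documents give no value for *f*, *m*, the 80% or the 16 points.

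**The case against.** The case against is substantial, and most of it limits the size of the point.

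- **Nobody is told to stop.** Section 6.6.3 gives a period of advised use; it does not ask participants to stop or to return the device. Section 6.6.2 refers to managing devices after primary outcome data are collected, and 6.6.5 has diaries collected on or after day 5 post randomisation, or at earlier discharge. Staff may well work to the randomisation clock. This stands: actual use may continue past the advised end.
- **The 48-hour case stacks two outer tolerances.** Section 6.6.1 wants prompt issue and 7.3 stresses early intervention. With the one to four hours of consideration time that 7.3 expects in the emergency department, the gap for many patients may be a matter of hours. This stands, and is why the case is called probably uncommon.
- **The schedule is in days, not hours.** Someone randomised early on Day 0 and taught late on Day 2 is more than 48 hours on. This stands; the hour figures are approximate on either clock.
- **Three adherent days can still be reached** in the 48-hour case, on one of the two ways of counting. This stands.

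A reader might infer that the primary comparison is biased, that the trial is materially underpowered, or that late-taught participants cannot count as adherent. The documents support none of these. The estimand follows a treatment policy approach regardless of compliance, the power and complier figures rest wholly on assumed inputs, and adherence remains attainable.

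What the objections do not remove is the mismatch itself. It exists even with immediate teaching (96 hours advised against 120 when randomisation is at 24 hours and *a* = 0), and no section resolves it.

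**Conclusion.** The point holds as a mismatch of clocks in a participant instruction, worth correcting but not serious. Advised use ends before the outcome window closes by the injury-to-randomisation interval: up to 24 hours after admission, plus whatever time passed between injury and admission. In the permitted worst case with admission at injury, about 48 hours of advised use remain against the stated 72-hour minimum, and later presentation lowers this further.

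The intention-to-treat comparison remains unbiased. The consequences are a possibly smaller dose late in the outcome window and less slack against the three-day adherence rule. The sizes of any power loss and any inflation of a complier estimate are unknown: there is no power loss if participants carry on or if benefit persists, and the complier analysis is only under consideration. The conclusion rests on reading the five days in 6.6.3 literally and the +2 tolerance as 48 hours; the injury-to-admission times shown are assumptions.

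**What to change.** In 6.6.3, change the end point of the advice so that participants are advised to use the device until 5 days after randomisation. Make the same change in the leaflet, video and diary wherever they carry the injury-based wording. Align the plain-English summary (3.1), which counts from arrival in hospital, to the same clock; otherwise a third starting point remains.

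With first teaching within 48 hours of randomisation, this leaves at least about 72 hours of advised use, in line with the stated minimum, and covers the whole outcome and adherence window. The teaching tolerance, eligibility, sample size and diary collection can stay as they are.

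The cost is a short wording change, with an amendment if the protocol and materials are already approved. Some participants will be advised to use the device for a day or so longer.
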